Real-world Evaluation of JBA GlucoTrojan with Reducose ® on Glycemic Response

NCT not assigned yet Date: July 8 2024

Real-world Evaluation of JBA GlucoTrojan with Reducose[®] on Glycemic Response

Summary

The project is focused on evaluating the real-world efficacy of JBA GlucoTrojan, a powdered supplement sachet containing Reducose, a natural water extract of White Mulberry Leaf, which has been scientifically proven to reduce the absorption of sugars and carbs by up to 40%. The study aims to compare the effect of consuming GlucoTrojan with a meal (Test Meal) vs. having the meal alone (control) on the blood sugar response of 50 healthy adults, pre-diabetes, or non-insulin dependent diabetes, over a period of 14 days. It is expected that GlucoTrojan will reduce the incremental area under the curve and the peak for plasma glucose concentration over 120 minutes in normoglycemic adults when compared to the response to a control meal.

Sponsor: *AQP Pharmaceuticals, Inc.* Contract research organization: Tastermonial Inc Principal investigator (PI): [name]. Co-investigator: [name], CEO

About Tastermonial

Food and supplement brands use the Tastermonial Platform to substantiate metabolic health claims by collecting data-driven insight from members of the public in a cost-effective manner.

Tastermonial consists of scientists and engineers who are passionate about conducting citizen scientist studies to help companies and their partners examine the efficacy of their product(s) via continuous-glucose-monitors (CGMs) and other biofeedback data sources. The results generated from our real-world studies are used to substantiate claims, drive consumer trust and brand loyalty, guide product development decisions, and de-risk clinical trials.

Disclaimer:

Please note that although Tastermonial conducted their studies in a real-world scenario and collected trustworthy data, these experiments were not conducted in a controlled setting, such as a laboratory, and the information does not hold any formal research significance.

Background

AQP Pharmaceuticals, Inc. ("Company") developed a powdered supplement sachet that can be added to meals targeting consumers who follow carbohydrate-heavy Asian diets. The product is formulated with the

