patented ingredient, "Reducose[®]", a natural water extract of novel White Mulberry Leaf that has been scientifically proven to reduce the absorption of sugars and other carbs by up to 40%. The effects have been confirmed previously via Randomized, Double-Blind, Controlled Trials (see Appendix I and II).

The Company is looking to conduct a real-world study of blood glucose responses to JBA GlucoTrojan (see specifications here) with a 5% concentration of Reducose[®]. The study will observe the real-world efficacy of GlucoTrojan when taken with high carbohydrate meals.

The Company wishes to use the collected data to showcase the comparative glycemic impact as well as testimonials from participants to build trust and loyalty with their customers.

Rationale

Reducing the health impact of dietary sugar intake is a public health priority. Mulberry leaf extract may reduce blood glucose responses following sugar intake by reducing gastrointestinal carbohydrate absorption via alpha-glucosidase inhibition activity of iminosugar constituents such as 1-deoxynojirimycin (DNJ). Mulberry leaf extracts are widely consumed in Asia for normalizing post-prandial blood glucose. Reducose has been tested in multiple clinical trials and lowers the postprandial glucose response by up to 40% (see Appendix).

Hypothesis

An appropriate dose of GlucoTrojan when co-administered with a complete meal will reduce the incremental area under the curve and the peak for plasma glucose concentration over 120 minutes in normoglycaemic adults when compared to the response to a control meal.

Study Objective

To compare the effect of consuming GlucoTrojan (mulberry-extract formula) with a meal (Test Meal) vs. having the meal alone (control) on the blood sugar response of 50 healthy (non-diabetes) adults, pre-diabetes or non-insulin dependent diabetes (Tester). Experiments will span 14 days.

Materials and Methods

Design

Testers will be given sachets of GlucoTrojan and standardized test meals. The experiment is conducted by logging foods on the Tastermonial app and syncing the continuous glucose data from the monitor into the

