Tastermonial app. Participants use the Tastermonial mobile iOS app to log what, when, and how they ate the tested product. The participants are instructed not to make changes in their usual diet and physical exercise during the study period. Additionally, participants are asked to note any medications or activities that can impact their postprandial glucose readings. The app is also used to collect qualitative data.

During the study period, each tester will be wearing a continuous glucose monitor (CGM) from Abbott Freestyle Libre (Link) to actively track their postprandial glucose responses for each meal. The Freestyle Libre measures interstitial glucose levels throughout the day and gives back data in 15-minute intervals, transmitting the results via an NFC receiver in a smartphone. Sensor memory limitations require the device to be scanned every 8 hours. Of note, CGM devices measure interstitial glucose levels (glucose from the fluid in between cells) While interstitial glucose and blood/plasma glucose levels correlate highly, they do not precisely show the exact same reading and incur a lag of about 2-7 minutes (as reported by the manufacturer here). Medical diagnoses are not made from interstitial measurements.

Participants enrollment

A total of 50 individuals will be recruited via the Tastermonial database and ambassador network. A study-specific online pre-screener (see appendix III) will be used to preliminarily identify potential subjects for the study. Information and guidance will be made available electronically and via our Trial Manager. Participants can ask questions to our staff via email, telephone calls, and video meetings. The Tastermonial platform will be used to manage the HIPAA-compliant data collection process.

Written informed consent for inclusion will be obtained digitally from all subjects before enrollment (check for a separated document). Participants will then conduct the study at home.

The sequence of events for the participant is as follows:

- Eligibility pre-screening based on a self-declared answers to questionnaire filled electronically by participants

- Informed consent signing

- Issuance of a CGM 14-day prescription (Rx) to the participant for it to be filled and the CGM picked up at their local pharmacy

- Shipment of Tastermonial test box containing 2 portions of the standardized test meals, the test instruction postcard and 15 sachets of GlucoTrojan with a 5% concentration of Reducose[®]

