- Participants follow the self-service onboarding guide and step-by-step test instructions by scanning the QR code on the postcard found inside the Tastermonial box

- Participants apply the CGM and wait 1 day before starting the test

- Participants start the protocol and follow day-by-day instructions for the next 13 days
- Participants are asked to complete the product feedback surveys.

Inclusion & Exclusion criteria

Inclusion criteria:

- Consent to study protocol
- BMI: 18.5 to 29.9 kg/m2

• 21 to 75 years old

Exclusion criteria:

- Physician-diagnosed T1D and insulin-dependent T2D
- Taking medications that modulate blood glucose response or control blood pressure other than Metformin
- An underlying health condition that warrants non-participation
- Individuals who are pregnant
- Any other dietary restrictions that prevent them from consuming study foods
- Unable to follow remote guidance via the Internet or smartphone
- Unable to follow controlled diet instructions
- Unable to use a CGM (Continuous Glucose Monitoring Devices)

Withdrawal or Discontinuation of Study Participation

Participants are entitled to withdraw from the study at any point. In addition, the principal investigator has the authority to remove a participant due to medical concerns or if the participant no longer fulfills the study's inclusion and exclusion criteria. It is the participant's responsibility to inform the study personnel if they believe they no longer meet the criteria while participating. The sponsor reserves the right to pause, delay, or terminate the study if necessary.

Timeline

From study kick-off to completion, the investigators anticipate that the entire study will take in total about 7-10 weeks depending on how fast feedback is provided. Inclusion and exclusion criteria of the study will influence the recruitment time. During the study, the investigators will support ad-hoc requests from the Company to review incoming test results, provide a prompt update, and provide marketing assets from the comparative results of individual testers per request.

Prior to commencing the creation of study material and the recruitment, the Company shall agree on the above elements of the study design. The company may work with Tastermonial to co-develop an additional testing guide to fulfill new hypotheses and collect more data.

The investigators anticipate the following timeline after the investigators agree on the test design and protocol:

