- Creation of study material e.g. ICF, study questionnaires, pre-screeners, digital protocol, and onboarding materials: 1-2 weeks*
- Enrollment of participants: 2-3 weeks
- Conducting the study: 2 weeks
- Data analysis & Report: 2 weeks

Execution plan

The investigators will carry out a within-subject comparative, open label study on enrolled participants. The experimental protocol is as follows:

Day 1: Start wearing the CGM sensor and let it self-calibrate for 24 hours

Day 2: Consume 1 serving of Test Meal for breakfast. Log the meal in the Tastermonial app.

Day 3: Consume 1 serving of Test Meal with GlucoTrojan for breakfast. Log the meal in the Tastermonial app.

Days 4-8: Participants will be instructed to take GlucoTrojan twice per day. Once during their typical breakfast meal and once during their typical dinner meal. Each breakfast and dinner will be logged in the Tastermonial app.

Days 9-13: Participants will continue with their typical lives but continue to log meals — breakfast and dinner — in the Tastermonial app.

Day 14: The experiment ends

On Day 1 and Day 2, testers must avoid eating foods or drinking anything except water after 10 PM and until 6 AM. At the start of each test, the investigators will ask testers to confirm that their blood glucose is within the typical resting range (70-100 mg/dL). If their blood glucose is not within the resting range, the investigators will ask testers to wait and check again in 15 minutes before starting the experiment. The test meal must be consumed within 10 minutes.

General instructions that apply from Day 1 to Day 14:

- 2 hours before the required action, refrain from strenuous exercise
- 2 hours after the required action, avoid other foods and refrain from strenuous exercise
- Use the proprietary Tastermonial smartphone app to scan the barcode or manually log test products and meals to record the serving size as they start eating. All events outside of the instructed ones should be noted in the food log.
- The context for each experiment should be consistent. E.g., if black coffee or tea is consumed within 2 hours after the required action, it should be consistently consumed for all experiments.

Data Handling & Analysis

Data Collection

The entire 14-day historical blood glucose data from the participants will be made available for analysis. The 2-hour postprandial blood sugar readings within a 15-minute interval will be analyzed, as well as the time-in-range of participants.

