Each participant's eating period (called a "meal") is normalized and overlaid in a data frame that captures glucose values over the course of the test. Several other metrics are computed, such as maximum and minimum values, standard deviation, and others. In particular, the investigators compute the iAUC ("incremental area under the curve"), a measure of the total amount of postprandial blood glucose level increased over the entire 2-hour period after eating. The methodology of iAUC calculation follows the gold standard used in the measurement of the glycemic index. The iAUC metric allows our team to easily compare and rank testing results, as well as compare against the pure sugar responses or the sugar tolerance test of an individual.

Data from each user is analyzed by our team and verified by a practitioner and a statistician. The raw Libreview data is annotated by the timestamps and the food log generated through the Tastermonial app.

Summary of obtained data

- A Glycemic Impact Exploratory Data Exports file in .xlsx/.csv format:
 - Anonymized blood glucose analysis including time-in-range
 - Per individual
 - Per experiment log
 - Metrics including iAUC, time to peak, peak (mg/dl), indicative GI & GL
 - Anonymized food log data
 - Anonymized tester profile and demographics data
 - Statistical Significance Analysis P-Value, Mean, Std Deviation at 95% confidence level

An example is shown below:

Limitations of the study and disclaimer

The investigators suggest the Company to not draw any final conclusion from the statistical analysis illustrated above, given the nature of this real-world observational study. A notable advantage of using this system is that volunteers are tested in real-world conditions. However, the test subjects were not under strict research testing conditions which could have caused a variance in the data generated. Further studies are required to further confirm our findings. As opposed to the randomized control trial studies, the collected data should provide a basis to further observe the different use cases, contexts and the customer profiles that the Company can market to.

Categorization of Study Risk and Dietary Supplement Safety

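### The Test Meal is eaten alone on Day 2 and with GlucoTrojan on Day 3 by everyone, once each, so the product effect cannot be separated from a day or order effect

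*Protocol*

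**What the plan says.** The Execution plan in the Protocol describes an open-label, within-subject study with one schedule for all participants. The control meal comes first ("Day 2: Consume 1 serving of Test Meal for breakfast") and the product meal comes the next morning ("Day 3: Consume 1 serving of Test Meal with GlucoTrojan for breakfast"). Under Participants enrollment, the supply is "Shipment of Tastermonial test box containing 2 portions of the standardized test meals", which is one per condition with none left for a repeat. No second sequence, randomised order or parallel control is described.

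The Hypothesis is causal: GlucoTrojan "will reduce the incremental area under the curve and the peak for plasma glucose concentration over 120 minutes". The deliverables under Summary of obtained data include "Statistical Significance Analysis P-Value, Mean, Std Deviation at 95% confidence level".

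Two passages limit interpretation. The Disclaimer at the front says that "the information does not hold any formal research significance". The Limitations section says "The investigators suggest the Company to not draw any final conclusion from the statistical analysis illustrated above" and contrasts the study with randomised controlled trials. Neither mentions meal order, day or sensor age.

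**The concern.** The study objective is the contrast between the meal with GlucoTrojan and the meal alone. Because the control is always on Day 2 and the product always on Day 3, anything that differs systematically between those two mornings goes into the estimate. Candidates visible in the Protocol are sensor age (about one day against about two days after application), a second exposure to the same meal, and changed behaviour on the day the participant knows the product is being taken.

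Such a shift could create an apparent benefit or hide a real one. With p-values reported against a causal hypothesis, a reader would naturally credit the whole difference to the product. A paired analysis removes stable differences between people. It does not remove a difference between days that everyone shares.

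**Working it through.** **Inputs.** From the Protocol: 50 participants; one control meal (Day 2) and one product meal (Day 3) each; the same order for all; 95% confidence level. Assumed, because the Protocol gives no figure: a two-sided test at 5%, the day shift d and the product effect, both in SDs of the paired differences. The Protocol gives no power or effect-size calculation to reproduce.

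**1. Can the two effects be separated?** Write each reading as participant effect + τ × (product taken) + π × (Day 3). Under the stated schedule, product taken = 1 exactly when day = 3, so those two columns are identical. With 50 participant columns plus one for product and one for day, the design matrix has rank 51 for 52 columns, and only τ + π can be estimated. With 25 people in each order it has rank 52 of 52, and τ and π are both estimable.

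**2. Rejection rates under the fixed order.** The paired t-test is significant once the observed mean difference reaches t(0.975, 49)/√50 = 2.010/7.071 = 0.284 SD. With a true product effect of zero and a day shift d, the test statistic is noncentral t with 49 df and noncentrality d√50:

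| Assumed shift d (SD) | False significant result, 50 pairs | Same, 30 pairs |
|---|---|---|
| 0.05 | 6% | 6% |
| 0.1 | 11% | 8% |
| 0.2 | 28% | 19% |
| 0.3 | 55% | 36% |

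The 30-pair column is an assumed lower count, to allow for withdrawals and excluded tests. For a fixed d, more participants make the false-positive rate worse, because the bias stays while the standard error shrinks.

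The shift can also mask an effect. A true effect of 0.4 SD has 79% power with 50 pairs. With an opposing shift of 0.2 SD the net difference is 0.4 − 0.2 = 0.2 SD, and power falls to 28%.

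**3. Randomised order, 25 per sequence.** The mean Day 3 minus Day 2 difference is τ + π in the control-first group. In the product-first group it is −τ + π + cτ, where c is the fraction of the product effect carried into the next day's control meal. Half the difference between the groups is τ(1 − c/2), so π cancels. Its standard error is ½√(1/25 + 1/25) = 1/√50 SD, the same as for the paired test, with 48 instead of 49 df.

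- No product effect, day shift 0.3 SD: 5.0% false positives (4.98% in 40,000 simulated runs).
- Effect detectable with 80% power: 0.404 SD under either design, if there is no carry-over.
- True effect 0.4 SD, by assumed carry-over:

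| c | Expected estimate (SD) | Power |
|---|---|---|
| 0 | 0.40 | 79% |
| 10% | 0.38 | 75% |
| 25% | 0.35 | 68% |
| 50% | 0.30 | 55% |

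**4. Does iAUC protect against sensor shifts?** Only partly. On an assumed nine-point curve, adding 8 mg/dL throughout leaves iAUC at 3052.5 but moves the peak from 130 to 138 mg/dL. Multiplying by 1.08 moves iAUC to 3296.7 and the peak to 140.4 mg/dL. A constant offset thus cancels in iAUC but not in an absolute peak, and a proportional drift cancels in neither.

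**The case against.** The strongest reply is that no shift has been shown. The documents give neither its size nor its direction, every percentage above rests on an assumed value, and at small shifts the inflation is modest. The Protocol also standardises the two mornings: the same overnight fast, a starting-glucose check, a time limit for the meal, limits on exercise and other food, consistent context, a baseline validity check, and a run-in ("Participants apply the CGM and wait 1 day before starting the test"). Control-first has a real advantage as well, since the product cannot carry over into the control meal. And the Protocol calls itself observational, sets itself apart from randomised trials and advises against final conclusions.

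Much of this stands, and it bears on weight. The standardisation plausibly narrows the day effect, the size is unknown, and the carry-over trade-off is genuine. None of it answers the point, however. The controls make each meal more uniform but do not vary the order, so a remaining shift would be neither visible nor removable. The limitations speak of variance from uncontrolled conditions, which is noise; a fixed order can produce bias, and the reader is not told that order and treatment coincide.

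The later blocks do not rescue the comparison. Product days (4–8) precede off-product days (9–13), the reverse of the test-meal order, so agreement in direction would give weak support. But those are participants' own meals, the block order is again the same for everyone, and the Protocol states no formal contrast between the blocks.

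**Conclusion.** The concern holds. For the comparison that is the study objective, product and day are completely confounded by the schedule itself, so no analysis plan can repair it. This conclusion needs no assumption about numbers.

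The practical size is unknown. It is illustrated by false-positive rates of 11% to 55% for assumed shifts of 0.1 to 0.3 SD with 50 pairs, and lower rates with fewer pairs. Those figures assume a two-sided 5% paired t-test and roughly normal differences.

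It should be fixed, because the main contrast is affected and the remedy is cheap. It is not graver than that, because no shift is demonstrated and the Protocol already disclaims definitive conclusions.

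**What to change.** Randomise participants 1:1 to control-first or product-first for the Day 2 and Day 3 breakfasts, using two versions of the existing app and QR-code instructions. Analyse the meals as a two-period crossover with a period term, and state the assumption of no carry-over across the one-day gap. Word the Day 2 instruction so that the first test meal cannot start before the 24-hour wait is complete; a breakfast label does not by itself guarantee that.

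The cost is a second instruction set and one model term. The downside is that half the sample takes the product the day before the control meal. Carry-over would pull the estimate toward zero, and a two-sequence, two-period design cannot test for it cleanly. Randomised order also does not remove expectation effects in an open-label study.

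If the fixed order is kept, add one sentence to the Limitations section saying that treatment and day coincide, and do not attribute the Day 3 minus Day 2 difference to GlucoTrojan alone. In either case, report any comparison of Days 4–8 with Days 9–13 as descriptive unless the block order is also randomised.

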Additional demographic profiles of participants will be collected and analyzed, including clinical parameters (age, sex, body weight, height, body mass index, meal composition; i.e.,calories, carbohydrates, fats, proteins, and fiber) and individual resting glucose range (Baseline Glucose Range) to determine their glycemic cohort.

The investigators will also collect qualitative data. Participants will be asked to report their feelings such as mood and well-being during and after the experiments in an online questionnaire. The questionnaire will be finalized with the approval of the company.

Data management

All documents relevant to the study, including completed ICFs, are hosted on a secure online portal. The ICFs are completed using a secured data transfer system on the HIPAA-compliant online portal. The company has access to the de-identified data set. The data is saved to a secured internal network. All data is anonymized during the analysis. HIPAA relevant PHI data privacy of participants is ensured on a secured online portal that uses the HIPAA compliant AWS servers. All participants are de-identified and labeled using a coding system.

Test Validation Methods

To ensure that the test was conducted under ideal conditions, e.g. on an empty stomach, the investigators rely on the participant's computed "baseline" or resting glucose average value, calculated as the average of all their glucose values from 1 AM to 4 AM each morning over the lifetime of the sensor. If the test was started far above the individual's **baseline range**, the test is considered an outlier and excluded from our initial analysis. This methodology was reviewed by a registered dietitian and a statistician.

The Baseline range

The baseline range of each individual is computed between 1 AM to 4 AM each morning over the lifetime of the sensor.

Several studies performed specifically using continuous glucose monitors suggest that a non-diabetic, healthy individual can expect:

- Maximum baseline range should not exceed 102 mg/dl for average non-diabetic testers
- ✤ Mean post-meal glucose peaks ranging from 99.2 ± 10.5 to 137.2 ± 21.1 mg/dl
- Time to post-meal glucose peak is around 46 minutes 1 hour
- Fasting glucose levels between 80-86 mg/dl

These are not standardized criteria or ranges but can serve as a simple guide for what has been observed as normal in individuals without diabetes.

iAUC Calculation

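### Product and period coincide in the free-living blocks: everyone is on product in Days 4-8 and off it in Days 9-13, so comparing the blocks cannot isolate the product

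*Protocol*

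**What the plan says.** The Execution plan states the design: "The investigators will carry out a within-subject comparative, open label study on enrolled participants". It then sets one schedule for everyone. After a sensor day come two standardised breakfasts, without product on Day 2 and with it on Day 3. Next: "Days 4-8: Participants will be instructed to take GlucoTrojan twice per day". The meals are the participant's own: "Once during their typical breakfast meal and once during their typical dinner meal". The last block reads: "Days 9-13: Participants will continue with their typical lives but continue to log meals". Nothing in the protocol randomises or counterbalances the order, and there is no concurrent control.

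Under Participants enrollment, each person is sent "2 portions of the standardized test meals, the test instruction postcard and 15 sachets of GlucoTrojan". The sensor comes from one prescription: "Issuance of a CGM 14-day prescription (Rx) to the participant".

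Data Collection makes the full glucose record available and says that 2-hour postprandial readings and time-in-range will be analysed. Among the other data collected is "meal composition; i.e.,calories, carbohydrates, fats, proteins, and fiber". Summary of obtained data lists p-values at a 95% confidence level. Design asks participants to keep their usual diet and exercise. The limitations section warns of extra variance from uncontrolled conditions and advises against final conclusions. It does not mention order, period or sensor age.

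**The concern.** Days 9-13 have no evident purpose except as the off-product counterpart of Days 4-8. Anyone given the data export will be inclined to set one block against the other and read the difference as the product's effect with everyday meals.

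That difference also contains whatever else changed between the first and second block: sensor age, calendar time, logging fatigue and food choice. The limits on exercise and other food are tied to a required action. In Days 9-13 the only stated action is logging, so those limits too may be followed differently in the two blocks.

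This is separate from the order of the Day 2 and Day 3 standardised meals. Counterbalancing that pair would leave the blocks as they are. At stake is any statement about the product with self-chosen meals. Background and Timeline say that comparative results will be shown to customers and used in marketing.

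**Working it through.** The protocol gives no effect size, standard deviation or power for this comparison, so there is no figure to reproduce. The check is structural, followed by illustrations on stated assumptions.

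**1. The two blocks side by side** (Execution plan, Participants enrollment)

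| | Days 4-8 | Days 9-13 |
|---|---|---|
| Product | breakfast and dinner | none instructed |
| Position | first, for everyone | second, for everyone |
| Meals | self-chosen | self-chosen |
| Sensor age in days | 4-8 | 9-13 |

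Both standardised portions are used on Days 2 and 3, so 2 - 2 = 0 remain for Days 4-13. The schedule uses 1 + 5 × 2 = 11 sachets and 15 are shipped. Four are therefore left during the off block, and its text does not expressly exclude their use.

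**2. What the comparison estimates.** Let τ be the product effect (on minus off) and π the period effect (second block minus first).
- First-block mean: μ + τ
- Second-block mean: μ + π
- On minus off: τ - π

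In a two-block model, the rows for intercept, product and period are (1, 1, 0) and (1, 0, 1). The rank is 2 for 3 parameters, so τ and π cannot be estimated separately.

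**3. Modelling a linear day trend instead.** Over Days 4-13 the mean day is 8.5 with variance 8.25. The product indicator has mean 0.5 and variance 0.25. The covariance is (4+5+6+7+8)/10 - 8.5 × 0.5 = 3.0 - 4.25 = -1.25.
- Correlation: -1.25 / √(8.25 × 0.25) = -0.87
- Variance inflation: 1 / (1 - 0.87²) ≈ 4.1, which about doubles the standard error

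The effect becomes estimable, but only on the assumption that the trend is linear.

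**4. Size through diet.** Assume iAUC is proportional to carbohydrate, and let c be carbohydrate in the on block relative to the off block. Apparent reduction = 1 - (1 - true reduction) × c.
- No effect, c = 0.9: 1 - 1.0 × 0.9 = 10%
- True 20%, c = 0.9: 1 - 0.8 × 0.9 = 28%
- True 20%, c = 1.1: 1 - 0.8 × 1.1 = 12%

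**5. False-positive rate.** Assume no product effect, a two-sided 5% paired t-test, n = 50 with complete data, and a block-to-block drift of d standard deviations of the within-person difference. The noncentrality is d√50; for d = 0.2 it is 1.41.

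| d | 0 | 0.1 | 0.2 | 0.3 | 0.4 | 0.5 |
|---|---|---|---|---|---|---|
| Rejects | 5% | 11% | 28% | 55% | 79% | 93% |

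Simulation (20,000 runs each at d = 0, 0.2, 0.3 and 0.5) agrees. The drift sizes are assumptions.

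**6. With the block order randomised, 25 per sequence.** The on-first group estimates τ - π and the off-first group τ + π. Their average is τ. The standard error is σ√(2/25)/2 = σ/√50, the same as for the fixed-order paired test. In the simulations with no product effect, bias was about 0 and the rejection rate 4.9% to 5.1% for drifts of 0 to 0.5. Carry-over was assumed absent.

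**The case against.** The strongest reply is that this comparison is not in the protocol. The Hypothesis concerns a control meal over 120 minutes, which fits the Day 2 and Day 3 pair. Data Collection does not say what is compared with what, and an SAP that is not shown may define it. That stands: the block comparison is inferred. But an SAP can choose the contrast and the model; it cannot change an order that everyone has already followed.

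A reader might also infer that no model could help. That goes too far. Meal composition is logged. Test Validation Methods uses glucose from 1 AM to 4 AM each morning, which can reveal a shift in sensor level. A constant offset largely cancels in iAUC, though a change in sensor gain would not, and time-in-range has no such protection. Lunches, if logged, could serve as an unsupplemented reference in both blocks. These are partial handles, each resting on its own assumption, and the protocol describes no adjustment that uses them.

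The standardised pair runs off then on, and the blocks on then off, so a steady drift would bias the two contrasts in opposite directions. This is a fair check but a weak one. With a drift of b per day, the pair is shifted by +b (one day apart) and the blocks by -5b (midpoints Day 6 and Day 11). It also says nothing about changes in self-chosen food.

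Finally, the protocol calls its export exploratory and advises caution. But the caution concerns variance, whereas a fixed order produces bias, and the same export lists p-values.

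**Conclusion.** The point holds as a limit on interpretation built into the schedule. If Days 4-8 are compared with Days 9-13, product and period are the same contrast, and the available data could separate them only in part. The bias may exaggerate or hide an effect. Its size cannot be had from the documents: the 10% carbohydrate shift and the drift sizes are illustrations, and participants are told to keep their usual diet.

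Three stronger readings are not supported. The protocol does not declare the block difference a formal efficacy test. Days 4-13 are not the only real-world part, because the whole study is run at home; they are the only part with self-chosen meals. Nor does anything show that drift will occur or that it would favour the product.

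The conclusion rests on reading Days 9-13 as the off-product comparator, which the comparative design, the 14-day analysis and the p-value output make the natural reading. It merits a change because the remedy is cheap.

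**What to change.** Randomise participants 1:1 to on-block-first or off-block-first for the two free-living blocks, using two versions of the QR-code instructions. Name the comparison in the protocol. Analyse it within person with period and meal type (breakfast or dinner) in the model. Use logged carbohydrate as an adjusted or sensitivity analysis, because in an open-label study food choice may itself respond to knowing that the product is being taken.

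The cost is a second instruction set and an allocation list, with no more participants, meals or sensor days. The analysis must assume negligible carry-over between blocks, which the protocol does not discuss. Randomising the order removes period bias; it does not remove open-label changes in behaviour.

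The sachet count and the Days 9-13 text should also be reconciled, so that it is clear what the off block means.

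If the order stays fixed, report Days 4-13 descriptively, with no p-value or efficacy claim from the block comparison, and name order and sensor age among the limitations.
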